- 4) Patients will be randomized by a random numbers system generated with a computational software and will be assigned to a group: 1) metformin (2 g/day) or 2) metformin (2 g/day) and dapagliflozin 10 mg. All patients will receive dietary treatment and follow-up during the study by Nutrition service. Dietary treatment is individualized, as it is based on the initial weight of the patient and their eating habits at the time of valuation. It is expected that dietary treatment does not influence the results because all patients will undergo diet and those with little attachment (defined as failure to comply with at least 80% of the prescribed diet) are discharged of the surgical protocol. The Nutrition service calculates the percentage of adherence to diet.
- 5) Once assigned to the corresponding group, patients will receive an identification code that will be retained throughout the study. One of the researchers not directly involved in patient care, will assign tablets needed for daily intake for a month and then the number of tablets required for 3 months in a sealed envelope.
- 6) A run-in period will be used to assess tolerance to treatments. This period will be for a month. At this time patients will be advised of a possible increase on urea and will be instructed in the relevance of increasing fluid intake.
- 7) The anthropometrical and biochemical variables will be recorded at baseline and at 1, 3, 6 and 12 months (Appendix 2. Data Collection Sheet). A clinical nutritionist accredited as Level 1 Anthropometrist by the International Society for the Advancement of Kinanthropometry (ISAK) will assess the weight on a scale with a

maximum capacity of 300 kg and precision of 100 g; height using an stadiometer, and waist circumference using a fiberglass tape, according to the manual of procedures for nutrition projects of the Centro de Investigación en Nutrición y Salud de Instituto Nacional de Salud Pública [86], and also in accordance with the procedures manual for the assessment of clinical and anthropometrical measurements in the adult and elderly of the Ministry of Health [87] (Appendix 3. Clinical and anthropometric measurements).

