6. Use of drugs for weight control.
7. Untreated or uncontrolled hypothyroidism (defined through TSH higher than 4.2 μ U/ml)
8. Pregnant or lactating mother.
9. Tobacco use (in the last month)
10. Current use of steroids or nonsteroidal anti-inflammatory drugs

Withdrawal criteria

1. Becoming pregnant during the study
2. Tobacco use
3. Use of steroids during the study

Sample size

Weight loss after dapagliflozin treatment has not been previously used as primary outcome in randomized controlled trials (RCT) of patients with prediabetes or diabetes and grade III obesity. Zhang et al. performed a meta-analysis that included seven RCTs evaluating the effect of metformin combined with SGLT2-inhibitors (dapagliflozin 10 mg/day, canagliflozin 300 mg/day, empagliflozin 25 mg/day, or ipragliflozin 300 mg/day) vs. metformin (at doses of 1.5 to 3 g/day) with placebo on HbA1c; fasting plasma glucose; and body weight over 24 weeks, 1 year, and 2 years. The total sample was 2847 patients with a mean BMI of 31.7 ± 4.9 kg/m². After a year of treatment, the placebo-metformin control group showed a reduction in body weight of 1.1 ± 3.39 kg, whereas the SGLT-2 inhibitor-metformin group showed a 3.6 ± 4.22 kg reduction with a mean difference of -2.6 kg (-3.17 to -2.03 kg), $p < 0.0000$. Using these data, we calculated a sample size using a mean difference formula. With a power of 80% (alpha level of 0.05) in a two-sided T-test, the sample size required is 90 patients: 45 patients in the M group and 45 patients in the D/M group. The final sample size required is 108 patients: 54 patients in metformin and 54 patients in the dapagliflozin group, allowing for a 20% dropout rate.

Variable definition

Variable name	Variable Type	Scale	Conceptual definition	Operational definition	Units
INDEPENDENT VARIABLES					

Type of treatment	Qualitative, dichotomic	Nominal	Metformin is a biguanide with effect in cyclic AMP kinase that diminishes insulin resistance. Diabetes treatment guidelines consider it as the first line therapy. Dapagliflozin is an SGLT2 inhibitor that induces glycosuria and has been approved for monotherapy in patients with metformin intolerance and also as a second or third line therapy for diabetes.	Use of metformin 2 grams per day or use of metformin 2 grams per day in combination with 10 mg of dapagliflozin.	0 = metformin, 1 = metformin/dapagliflozin
-------------------	-------------------------	---------	--	--	---

DEMOGRAPHIC VARIABLES

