Interleukine 10 (IL-10)	Quantitative continuous	Ratio	Anti-inflammatory cytokine related to the development of atherosclerosis	Concentration determined using the method ELISA.	pg/ml
Ghrelin	Quantitative continuous	Ratio	Hormone secreted in the gastric fundus that induces appetite.	Concentration determined using the method ELISA.	pg/ml

Glucagon	Quantitative continuous	Ratio	Hormone produced by pancreatic alpha cells that counteracts the effects of insulin.	Concentration determined using the method ELISA.	ng/ml
----------	-------------------------	-------	---	--	-------

Statistical analysis: Quantitative variables were described using measures of central tendency and dispersion according to the data distributions. Qualitative variables were described using frequencies or percentages. The Shapiro-Wilk test was used to establish normality in the distribution of quantitative variables. Because information on the different quantitative variables was available up to different time periods, a mixed model analysis was performed using the restricted maximum likelihood (REML) method, as well as a mixed model considering the fixed effects of assigned treatment, sex, and prediabetes or diabetes status, and the random effects of variability in weight loss over time. Comparisons between groups were analyzed using Sidak's post-hoc test. Pearson's chi-square test or Fisher's exact test were used to evaluate the association between qualitative variables. Statistical significance was defined as a $p < 0.05$. Data analysis was performed using SPSS version 17.0 and STATA version 11.0.

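### Arms are compared with Sidak's test, but neither the family it covers nor a primary time point is defined, so the single 5% one-year comparison behind the sample size is not identified in the analysis

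*Combined protocol and SAP*

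**What the plan says.** All references are to the combined protocol and SAP.

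- **Analysis (section 8, Statistical analysis).** Mixed models fitted by REML are planned. The fixed effects listed are treatment arm, sex and glycaemic status; time appears only in the random part. A REML mixed model is also mentioned without any terms. The between-arm procedure is one sentence: "Comparisons between groups were analyzed using Sidak's post-hoc test". The significance threshold is 0.05.
- **Sample size (section 8).** The calculation is framed as "With a power of 80% (alpha level of 0.05) in a two-sided T-test". Its inputs are one-year results from a meta-analysis: "the placebo-metformin control group showed a reduction in body weight of 1.1 ± 3.39 kg" and "the SGLT-2 inhibitor-metformin group showed a 3.6 ± 4.22 kg reduction". The result is "45 patients in the M group and 45 patients in the D/M group", raised to 54 per arm for dropout. No multiplicity adjustment enters.
- **Visits.** Workplan item 7 states: "The anthropometrical and biochemical variables will be recorded at baseline and at 1, 3, 6 and 12 months". The form in Appendix 2 has the same four post-baseline columns. The abstract and the weight entry in the variable table give months 3, 6 and 12 only.
- **Objective (section 6).** Weight loss is the lead outcome, with no time point attached.

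**The concern.** Sidak's method corrects for a family of comparisons. The design has two parallel arms, so at any one time point there is one between-arm contrast and nothing to correct. The adjustment matters only if the family extends over something else, most naturally the visits. The plan does not say.

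Two things are at stake. If the adjustment covers the visits, the trial is underpowered for the comparison it was sized for. If it is inert and no visit is declared primary, a significant result at any visit could be presented as the answer. That risk is practical here: under Workplan item 2, patients reach the weight loss needed for surgery at different times and their data stop before the operation, so early visits will tend to hold more patients than month 12.

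**Working it through.** **Inputs.** One-year changes of −1.1 kg (SD 3.39) and −3.6 kg (SD 4.22); two-sided alpha 0.05; power 80%; 45 evaluable per arm (all from Sample size). Post-baseline visits: k = 3 or 4.

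**Reproducing 45 per arm.** The plan does not say which SD was used. The difference of arm means is 3.6 − 1.1 = 2.5 kg. With the larger SD,

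n = 2(1.960 + 0.842)² × 4.22² / 2.5² = 44.7, rounded up to 45.

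This matches exactly. Other combinations do not: pooled SD √[(3.39² + 4.22²)/2] = 3.83 gives 37; the stated 2.6 kg with SD 4.22 gives 42; 2.6 kg with the pooled SD gives 35. I therefore take 2.5 kg and 4.22 as the sizing inputs. Power at 45 per arm is 80.2% (normal approximation) or 79.4% (noncentral t).

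**Reading A: the family is the visits.** The per-comparison level is 1 − 0.95^(1/k), which is 0.01695 for k = 3 and 0.01274 for k = 4. The noncentrality is 2.5 / (4.22 × √(2/45)) = 2.81 on 88 degrees of freedom. One-year power from the noncentral t:

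| Inputs | Unadjusted | k = 3 | k = 4 |
|---|---|---|---|
| 2.5 kg, SD 4.22, 45 per arm (sizing inputs) | 79.4% | 64.7% | 60.6% |
| 2.6 kg, SD 4.22, 45 per arm | 82.4% | 68.7% | 64.8% |
| 2.5 kg, SD 3.83, 45 per arm | 86.5% | 74.5% | 71.0% |
| 2.6 kg, SD 3.83, 45 per arm | 89.0% | 78.3% | 75.0% |
| 2.5 kg, SD 4.22, 54 per arm | 86.2% | 74.2% | 70.6% |

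Only by combining the pooled SD with no dropout at all (54 per arm) does adjusted power reach 80% or more (80–86%). On the sizing inputs, keeping 80% power at the Sidak level would need 60 (k = 3) or 64 (k = 4) evaluable per arm.

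**Reading B: Sidak within each visit.** One contrast per visit means no adjustment. The one-year test stays at 0.05 with about 80% power. If significance at any visit may carry the claim, the chance of at least one false positive for weight with independent tests is 1 − 0.95³ = 14.3% or 1 − 0.95⁴ = 18.5%. Visits in the same patient are correlated. The documents give no correlation, so I assume a common value. Simulation of equicorrelated normal statistics gives:

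| Assumed correlation | k = 3 | k = 4 |
|---|---|---|
| 0.5 | 12.5% | 15.7% |
| 0.8 | 9.8% | 11.4% |
| 0.9 | 8.3% | 9.3% |

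**Reading C: one overall treatment effect.** The listed fixed effects contain no visit or treatment-by-visit term. Taken literally, there is one treatment contrast per outcome, Sidak is inert, and there is one 5% test. That contrast averages over the available visits. It is not the one-year difference on which 45 per arm rests.

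**The case against.** The strongest reply is that the model as listed supports Reading C: a single treatment contrast at 5%, with no loss of level and no repeated looks. That stands as a possible reading, though it cannot be confirmed, because the terms of the other REML model are not given and a family over treatment-by-covariate cells or over outcomes is not excluded either.

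It is also fair to say that one year is implied as the main time point by the sizing inputs and the one-year follow-up, and that no text makes success at any visit a winning rule. If one year were declared primary, the excess false-positive rate under Reading B would disappear. Sidak over the visits would itself be valid; its price is power.

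Two limits on the figures also stand. The powers are for a t-test, while the planned mixed model uses partial follow-up, so its actual power is not established here. And the four-visit case is weaker than the three-visit case, since the variable table defines weight without month 1, which coincides with the end of the one-month run-in.

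What does not follow is that the plan is adequate. Each defence works by choosing a reading that the text does not choose.

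**Conclusion.** The point holds as an undefined family and an unnamed primary time point, set against a sample size built for one specific test. None of the readings examined makes the written analysis single out the one-year 5% comparison that was sized.

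The size depends on the reading. With Sidak over visits, power is about 65% (3 visits) or 61% (4 visits) on the sizing inputs, and 65–78% across the four alternative input sets tabulated. With Sidak inert within visits, one-year power is about 80%, and the false-positive rate for weight is about 8–12% (3 visits) or 9–16% (4 visits), but only if any visit may carry the claim and correlations lie between 0.5 and 0.9. With one overall effect, there is no inflation, but the quantity tested is different.

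A reader might infer that the trial simply has 61–65% power, that its error rate is at least doubled, or that the one-year comparison cannot be a 5% test under any reading. The documents support none of these. The first needs Reading A and the sizing inputs. The second needs a success rule that is nowhere stated, and fails at a correlation of 0.9. The third is wrong under Reading B.

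**What to change.** Reconcile the visit schedule first: months 3, 6 and 12 in the abstract and variable table, against months 1, 3, 6 and 12 in Workplan item 7 and Appendix 2.

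Then replace the Sidak sentence with wording to this effect: *The primary analysis is the difference between arms in weight change at one year, estimated from the mixed model with visit and treatment-by-visit fixed effects in addition to the terms already listed. It is tested once at two-sided 0.05 without Sidak adjustment. Differences at earlier visits are secondary, and Sidak's adjustment is applied to those only.*

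The Statistical analysis paragraph is written in the past tense. If the analysis has already been run, the sponsor should report which family was used and label this clarification as post hoc.

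The cost is wording and two model terms; no further patients or data are needed. There are two downsides. Earlier visits can no longer carry the claim. And for patients whose data end at surgery, the one-year estimate relies on the model, so the plan should state how the estimate is to be interpreted for them.

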4. ETHICAL ISSUES

For the realization of this protocol, we will apply for approval by the Instituto Mexicano del Seguro Social (IMSS) National Ethics Committee. The proposed procedures are compliant with ethical regulations, the General Health Law regarding Health Research, the institutional regulations for investigation, the declaration of Helsinki in 1975 and its amendments. It also is compliant with the currently approved international codes and norms regarding Good Clinical Practice in Clinical Investigation.

Risk: according to the General Health Law regarding Health Research, this study represents a "higher than minimum risk" for the participants since it is a clinical trial (Article 17).

Contributions and benefits of the study for the participants and society: patients will not be directly benefited from this study. This statement will be stipulated into informed consent form. Regarding utility of the study, in case that we can determine higher effectiveness of the combination of metformin with dapagliflozin in terms of weight control, glucose concentrations, blood pressure and triglycerides, we will be able to recommend its inclusion in the treatment for the metabolic control of patients with extreme obesity.

Confidentiality: Patient will be guaranteed that personal data will be kept confidential according to the Article 21 Fraction VIII of the General Health Law regarding Investigation Research.

Conditions under which the informed consent will be requested: The informed consent form will be requested before the inclusion of the patient in the study. The patients will be invited personally when they attend to their regular visits to the outpatient clinic. (See appendix 7. Informed Consent Form). The principal investigator and co-investigators will sign the consent.

The patient will be explained about the freedom to withdraw consent at any time during the investigation according to Article 21 Fraction I-VII of the General Health Law regarding Investigation Research.

Participant selection: all patients meeting the inclusion criteria and no exclusion criteria that sign informed consent will be included in the study.

11. RESOURCES AND ENVIRONMENT

Human resources. All the investigators participating in this study have expertise in clinical trials, they are trained in the management of the patients attending to the clinic and they are authorized to perform and handle blood samples and patient data.

The investigator group includes one attending physician registered in the obesity clinic in the Endocrinology department, which will also be in charge of this protocol as part of the work to achieve his Doctors degree in Science (D.Sc.); other members of the group are two attending general endocrinologists with experience in clinical investigation in obesity and two other endocrinologists from the Experimental Endocrinology Unit which constitutes the laboratory area of the Endocrinology department. These endocrinologists can perform the laboratory techniques required for this protocol and one of them has been previously involved in protocols with pharmaceutical companies.

Material resources. The investigation unit and the endocrinology department have the necessary equipment required for the procedures. We will apply for financing for the purchase of the ELISA kits as well as for some of the supplies required for the protocol.

Feasibility. According to the large number of patients existing in the Obesity Clinic that are waiting for bariatric surgery and the frequency of metabolic disturbances found in the extremely obese, we consider that the number of patients required for the study is feasible.

The clinical and laboratory investigators involved in this protocol have the necessary expertise for the management of patients with extreme obesity, taking blood samples and information gathering. The Investigation Unit has ample experience in the management of biological samples and analysis with ELISA. They have also performed studies in the field of immunoendocrinology.

11. APPENDIX

Appendix 1. Criteria for diagnosis of prediabetes and diabetes according American Diabetes Association (ADA) guidelines.

	Prediabetes	Diabetes
Glycated hemoglobin	5.7 - 6.4%	$\geq 6.5\%$
Fasting plasma glucose	100 - 125 mg/dl	≥ 126 mg/dl
Oral glucose tolerance test	140 - 199 mg/dl	≥ 200 mg/dl
Random plasma glucose		≥ 200 mg/dl

Considerations

1. The fasting glucose test must be performed after caloric deprivation for at least 8 hours.
2. Oral glucose tolerance test must be performed as follows:
 - a. The patient must have at least an 8-hour fasting.
 - b. Basal venous plasma glucose will be determined.
 - c. The test should be performed as described by the WHO, using a glucose load containing the equivalent of 75 g anhydrous glucose dissolved in water and a new serum glucose determination will be performed after two hours of the glucose administration.
 - d. The test will be considered invalid if the patient is not able to take the complete glucose load or if vomiting is present during the test
 - e. The test will not be performed in patients with a basal glucose higher than 200 mg/dl.
 - f. Glucose tolerance test is required for patients classified as prediabetic.
 - g. A random glucose higher than 200 mg/dl is a valid test only for patients with evident symptoms of hyperglycemia or hyperglycemic crisis.
 - h. The ADA recommends that all patients classified as obese by BMI should be tested for diabetes or prediabetes.

Appendix 2. Collecting data sheet
INSTITUTO MEXICANO DEL SEGURO SOCIAL

Name: _____
 Social security ID number: _____ Treatment
 code _____
 Birthdate: _____ Inclusion date: _____
 Direction: _____
 Phone number: _____ Gender: _____ Height: _____ Age: _____

Relevant history (Cross out the appropriate option)

Smoking (Yes) (No) Age from beginning: _____ Number of years _____

Cigarettes/day: _____

Alcoholism (Yes) (No) Age from beginning: _____ Number of years _____

Drinks/week: _____

Cancer history in family (father, mother, aunt, uncle, grandfather/mother) (Yes) (No)

Type: _____

Comorbidities	Yes	No	Age from diagnosis	Drugs (Frequency/doses)
Hypothyroidism				
Prediabetes				
Diabetes Mellitus				
Hypertension				
Hypertriglyceridemia				
Myocardial infarction/angina				
OSAH syndrome				

Osteoarthritis			

Labs	Initial	Final	Labs	Initial	Final
Glucagon (ng/ml)			Creatinine clearance (ml/min)		
Ghrelin (pg/ml)					
Adiponectin (pg/ml)			iPTH (ng/ml)		
Resistin (ng/ml)			Calcium (mg/dl)		
IL-6 (pg/ml)			Phosphorus (mg/dl)		
IL-10 (pg/ml)			Magnesium (mg/dl)		

Name: _____ NSS: _____

Parameter	1 month	3 months	6 months	12 months
Weight (kg)				
BMI (kg/m ²)				
Waist circumference (cm)				
Systolic blood pressure (mmHg)				
Diastolic blood pressure (mmHg)				
Glucose (mg/dl)				
HbA1c (%)				
TAG (mg/dl)				
TC (mg/dl)				
HDL-c (mg/dl)				
LDL -c(mg/dl)				
Urinary infection (y/n)				
Ketonuria (y/n)				
Proteinuria (y/n)				
Leukocyturia (y/n)				
Nitrite (y/n)				
Sodium (mEq/L)				
Potassium (mEq/L)				

Calcium (mg/dl)				
Phosphorus (mg/dl)				
Magnesium (mg/dl)				
Drugs (hypoglycemic agents, antihypertensives, treatment for dyslipidemia)				

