6. OBJECTIVES

- a. **Primary objective:** To determine if combined treatment with dapagliflozin and metformin is more effective than monotherapy with metformin for weight loss and assess its effects on waist circumference, triglycerides, blood pressure and inflammatory cytokines in patients with prediabetes and diabetes with obesity class III.
- b. **Secondary objectives:**
 - i. To determine efficacy of metformin monotherapy for weight loss and decrease on waist circumference, triglycerides and blood pressure in patients with prediabetes and diabetes with obesity class III.
 - ii. To compare efficacy of metformin monotherapy and combined treatment with metformin and dapagliflozin.
 - iii. To determine the percentage of patients that with combined treatment achieves a decrease in total weight of 5%, 10% and 15% and the percentage of patients that achieve a decrease in 10% of excess weight.
 - iv. To evaluate if combined treatment allows a decrease in number of drugs needed for comorbidities' control.
 - v. To evaluate prevalence of adverse effects commonly associated with dapagliflozin use (urinary and genital tract infections, hydroelectrolytic alterations) in patients with obesity class III.
 - vi. To determine serum concentration of adiponectin, resistin, IL-6, IL-10 and TNF- α before and after treatments, and compare it between groups.
 - viii. To determine serum concentration of insulin, glucagon and ghrelin before and after treatments, and compare it between groups.

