IL-6 was characterized as a pro-inflammatory cytokine secreted by adipose tissue. It has been linked with the downregulation of IRS-1 (insulin receptor substrate type 1), impaired phosphorylation of tyrosine kinase, and decreased expression of GLUT4 (glucose transporter 4). Additionally, it increases resistance and decreases adiponectin levels [73-75].

Interleukin 10 (IL-10)

It is also known as Cytokine-synthesis Inhibiting Factor (CSIF). IL-10 is a cytokine with anti-inflammatory properties due to their ability to inhibit the synthesis of pro-inflammatory cytokines from T-lymphocytes and macrophages. Its presence has been proven in human atherosclerotic plaques and it has been that its low concentration favors the development of larger and unstable atherosclerotic lesions [76].

Tumor necrosis factor alpha (TNF- α)

Initially, TNF- α was described as a pro-inflammatory cytokine released by macrophages and monocytes as part of the immune response. Soon after, its expression and release were discovered in adipocytes and was quickly linked to insulin resistance in rodents and humans with obesity. It is known that TNF- α is involved in several processes related with development of insulin resistance, such as [77-79]:

- 1) Reduces expression of GLUT4, consequently decreasing glucose caption in the cell.
- 2) Induces serine phosphorylation at insulin receptor, affecting signaling cascades.
- 3) Induces down-regulation of IRS-1.
- 4) Increases expression of IL-6 and leptin and decreases adiponectin expression.
- 5) It has been associated with adipocytes apoptosis through increased concentration of intra-cellular free fatty acids.

Security of dapagliflozin

Based on combined analysis of three clinical trials, it was observed that dapagliflozin did not cause hypoglycemia compared to other oral hypoglycemic drugs (OR 0.49, 95%CI 0.18 to 1.39). In fact, hypoglycemia rate was 10 times lower compared with sulfonylureas.

The most common side effect observed in patients treated with dapagliflozin is genital tract infection (OR 3.48, 95%CI 2.33 to 5.20): vulvar-vaginal mycotic infections in women and balanitis in men, none of whom was reported as serious or requiring treatment discontinuation. It was also observed an increase in the incidence of urinary tract infections (OR 1.43, 95%CI 1.05 to 1.94), which were reported as mild to moderate intensity, were more frequent in females and caused a low rate of discontinuation (0.3% vs. 0.1% with placebo) [80].

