- 8) The determination of blood pressure will be performed by a nurse from the Obesity Clinic, using an aneroid sphygmomanometer, recording the average of two measurements taken with a 5-minutes difference, according to the procedure's manual for the assessment of clinical and anthropometrical measurements in the adult and elderly of the Ministry of Health (Appendix 3. takes clinical and anthropometric measurements).
- 9) The determination of insulin, glucagon, ghrelin, adiponectin, resistin, IL-6, IL-10 and TNF- α will be held at baseline and before surgery (depending on the response of each patient). For the determination of these cytokines and peptides, an ELISA kit (enzyme linked immunosorbent assay) will be used (Appendix 4. ELISA technique).
- 10) Adherence to treatment will be evaluated and will consist in consumption of 90% of pills granted. The registration of adverse events will take place from the start of treatment and throughout the study. Each event will be evaluated by researchers and classified according to CTCAE list (Common terminology criteria for adverse events version 4.03). CTCAE considers that an adverse event grade 4 or 5 indicates discontinuation of treatment; grade 3 must be submitted to review by the medical team, and grades 1 or 2 require registration and intervention but not discontinuation of treatment (Appendix 5. CTCAE list). Adverse events will be recorded in the report sheet (Appendix 6. Sheet report for drug side effects).
- 11) The patients that do not achieve weight loss at one-year follow-up will be discarded to their primary care hospital as pre-specified by the Obesity Clinic internal regulation.

Selection criteria

Inclusion criteria

- 1. Age from 18 to 60 years
- 2. Any gender
- 3. BMI greater than or equal to 40 kg/m²
- 4. Diagnosis of diabetes or prediabetes according to the criteria of the ADA. Patients must have glycated hemoglobin less than 9%.
- 5. Patients who sign informed consent letter (Appendix 7. Charter informed consent)
- 6. Candidates to bariatric surgery

Exclusion criteria

- 1. Current use of insulin or sulfonylureas
- 2. Chronic kidney disease with glomerular filtration rate <60 ml/min/1.73 m²
- 3. Use of loop diuretics with no possibility to suspend.

4. Concomitant illnesses that predispose to volume depletion, weight loss (including oncological diseases), or metabolic acidosis (including drug users)
5. History of recurrent genital or urinary tract infections

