Appendix 6. Adverse event registry form

Adverse events (effects/reactions) presented by patients included in investigation protocols.

México City, _____, 20_____

I, [name], M. Sc. as the Principal Investigator of the protocol titled "Effectiveness of the treatment with dapagliflozin and metformin compared to metformin monotherapy for weight loss and its effects on waist circumference, triacylglycerol concentration, blood pressure and inflammatory cytokines on diabetic and prediabetic patients with obesity class III. Open, randomized clinical trial."

Registered number: _____

Date of authorization: _____

Site: **Hospital de Especialidades CMN SXXI**

Inform that I have reviewed each and every adverse event (effect/reaction) presented by the patients included in this investigation protocol. These events are described as follows:

Date	Case number	Reaction description	Outcome	Suspected relationship to the protocol intervention	Initial or follow up report

Please mark with an X one of the two options. In the cases where the second line is marked, please explain the motives:

After careful analysis, I declare that none of the adverse events described previously demands for suspension or cancelling of the investigation protocol.

Protocol has been suspended due to the following reasons:

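### The visit sheet prompts for urinary infection but has no item for genital infection, so the two infections in objective v are not collected comparably and genital infection may be under-counted

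*Combined protocol and SAP*

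**What the plan says.** Section 6, secondary objective v, is "To evaluate prevalence of adverse effects commonly associated with dapagliflozin use (urinary and genital tract infections, hydroelectrolytic alterations") in patients with class III obesity. Both infections sit in one objective.

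Section 7, on the safety of dapagliflozin, states: "The most common side effect observed in patients treated with dapagliflozin is genital tract infection", with an odds ratio of 3.48 (95% CI 2.33 to 5.20). For urinary infection it gives 1.43 (1.05 to 1.94). It names vulvovaginal infection in women and balanitis in men, and says that none of the genital infections was reported as serious or led to stopping treatment.

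The Appendix 2 visit grid has columns for months 1, 3, 6 and 12. Its rows include "Urinary infection (y/n"), ketonuria, proteinuria, leukocyturia, nitrite and five electrolytes. It has no row for genital infection and no baseline column.

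Section 8, Workplan item 10, covers adverse events in general: "The registration of adverse events will take place from the start of treatment and throughout the study". Each event is classified by CTCAE and entered on Appendix 6. That form has columns for date, case number, description, outcome, "Suspected relationship to the protocol intervention" and report type. Appendix 5 uses urinary, vaginal and vulvar infection as grading examples. Section 8 describes the trial as open.

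**The concern.** The visit sheet has rows for urinary infection and electrolytes, but none for the harm that the protocol itself expects most often. One component of objective v is recorded as yes or no for every patient at four fixed times. The other is recorded only when an event is identified and written on a free-text form. A blank on the sheet can be read as no urinary infection or as a missing entry; the absence of an Appendix 6 line cannot be told apart from a question that was never put.

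The events most likely to be missed are mild ones, and the Background describes the expected genital infections as not serious. Objective v asks for a prevalence, so missed events lower the estimate directly. Because patients and clinicians know the treatment, the chance that a genital symptom is mentioned, or recorded as an adverse event, may also differ between arms. No later analysis can recover events that were never recorded.

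**Working it through.** **1. Forms set against objective v**

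| Component of objective v | Item on the Appendix 2 visit grid | Other route |
|---|---|---|
| Urinary infection | Yes/no row at months 1, 3, 6, 12, plus leukocyturia and nitrite | Appendix 6 |
| Electrolyte alterations | Sodium, potassium, calcium, phosphorus, magnesium | Appendix 6 |
| Genital infection | None | Appendix 6 only |

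Genital infection is the only component without a structured item. It does have a recording route. What the documents do not show is a prompt.

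**2. How much capture could matter (illustration)**

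Inputs from the documents: odds ratio 3.48 (Section 7) and 54 patients per arm (Section 8, Sample size). Assumptions, because the documents give neither: control risk p0 from 1% to 10%, and capture fractions of 50% and 75%.

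Risk in the combination arm: p1 = 3.48·o / (1 + 3.48·o), with o = p0/(1 − p0).

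At p0 = 0.05: o = 0.05263; 3.48 × 0.05263 = 0.18316; p1 = 0.18316/1.18316 = 0.1548. Expected affected patients are 54 × 0.05 = 2.7 and 54 × 0.1548 = 8.4.

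With capture fractions c0 (control) and c1 (combination), the observed odds ratio is [c1·p1/(1 − c1·p1)] / [c0·p0/(1 − c0·p0)]. At p0 = 0.05:

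- c0 = c1 = 0.50: (0.0774/0.9226)/(0.025/0.975) = 3.27
- c0 = 0.50, c1 = 0.75: (0.1161/0.8839)/(0.025/0.975) = 5.12
- c0 = 0.75, c1 = 0.50: (0.0774/0.9226)/(0.0375/0.9625) = 2.15

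| Assumed control risk | Expected affected, control vs combination | Seen at 50% capture in both | OR, 50% in both | OR, 50% control / 75% combination | OR, 75% control / 50% combination |
|---|---|---|---|---|---|
| 1% | 0.5 vs 1.8 | 0.3 vs 0.9 | 3.44 | 5.20 | 2.29 |
| 3% | 1.6 vs 5.2 | 0.8 vs 2.6 | 3.35 | 5.16 | 2.22 |
| 5% | 2.7 vs 8.4 | 1.4 vs 4.2 | 3.27 | 5.12 | 2.15 |
| 10% | 5.4 vs 15.1 | 2.7 vs 7.5 | 3.08 | 5.02 | 2.00 |

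Equal loss in both arms lowers the prevalence in proportion and barely moves the odds ratio. Unequal loss moves the odds ratio up or down, depending on which arm is better captured.

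**3. What the trial could show with perfect capture**

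The two-sided 5% normal-approximation power for a difference between p0 and p1 with 54 per arm is 13%, 30%, 43% and 66% at control risks of 1%, 3%, 5% and 10%. With half captured in both arms it is 9%, 17%, 23% and 35%. The comparison is thin in any case, so the value of objective v lies mainly in an honest estimate of prevalence by arm.

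**The case against.** The strongest reply is that the plan already has a study-long route for every adverse event, with evaluation by the researchers and a free-text description. Two of the three worked examples in Appendix 5 are genital infections, so the harm was plainly anticipated, at least in women; there is no example for balanitis. This stands, and it limits what can be claimed.

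A reader might infer that genital infections will be under-counted, or that they reach the database only if the patient volunteers them. The documents support neither. They do not say how adverse events are elicited, and investigators may ask. The urinary row also sits beside urinalysis items, so it may be filled from a urine test rather than a question. What remains is that one infection has a fixed entry at four visits and the other has no documented prompt.

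A reader might also count the missing grade column on Appendix 6 as a cause of under-counting. It cannot lower a count, and a grade can be written in the description field. It bears only on severity and on tracing the grade-based rules.

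Nor can one assume that only the combination arm expects the event: consent precedes inclusion, so any risk information it contains reaches both arms before allocation. The direction of any bias is unknown. Finally, the exclusion of patients with recurrent genital or urinary infections may lower the baseline risk, so the smaller counts in the table may be the more realistic.

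**Conclusion.** The point holds in a limited form. Objective v joins two infections that the forms collect by different means, and the one without a structured item is the one the protocol expects most often. Genital infection may therefore be under-counted and cannot be read alongside urinary infection on equal terms. In an open trial, unequal capture could bias the arm comparison either way.

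The size is illustrative. For control risks of 1% to 10%, capture of 50% in one arm and 75% in the other would turn a true odds ratio of 3.48 into about 5.0 to 5.2, or about 2.0 to 2.3 if the arms are reversed. The control risks and capture fractions are assumptions. The matter touches one secondary safety objective; the weight outcome, sample size and significance level are unchanged. It is a cheap improvement to data collection rather than a flaw in the trial's main comparison.

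**What to change.** Add a row to the Appendix 2 grid asking whether a genital infection has occurred since the last visit (yes/no). Ask it of both sexes in both arms, with the same wording, at each scheduled visit, and add a baseline entry. Analyse objective v's infections by arm from the prompted items combined with the Appendix 6 reports, so that events logged between visits are not discarded.

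The cost is one more question per visit and a few more mild events on record. Recall would span up to six months between months 6 and 12, which is a further reason to keep the Appendix 6 reports in the count.

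Separately, add CTCAE term and grade columns to Appendix 6. Workplan item 10 attaches consequences to the grade ("CTCAE considers that an adverse event grade 4 or 5 indicates discontinuation of treatment"), and the form has no field showing which grade was assigned. This is for traceability only and changes none of those rules.

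If data collection is complete, report that the visit sheet did not prompt for genital infection, and interpret that comparison with caution.
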